6.6 ANALYSIS OF PRIMARY OUTCOME

The primary outcome will be analysed using a Poisson regression model (i.e. generalized linear model with a log link) to assess the differences between the two treatment groups (BUP-XR or MET/BUP-SL). The randomisation stratification variables (centre and current injecting status) will be included in the model as covariates. If a Poisson distribution is not observed then the regression model to be used will be dependent on the distribution of the data and decided following the decision tree in appendix 1, figure 1.

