6.8 SUBGROUP ANALYSES

Subgroup analyses will be conducted for the primary objective/outcome on the following:

- Using cocaine (Yes/No)
- Length of time in treatment (less than one month/one month or longer)
- Benzodiazepine use past month to admission (Yes/No)
- CGI-S (Mild/Severe)

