Sensitivity analysis will be conducted truncating at 14 days at the end of the TLFB data (i.e. day 8 – day 154) to assess the impacts of using the medical notes due to the administration error highlighted in section 5.2.

Furthermore, there will be a sensitivity analysis around the week 'Grace period' of the primary outcome where we will include all TLB data from day 0 to day 168.

COVID-19

A sensitivity analysis around the impact of the COVID-19 pandemic has been considered. The biggest impact the pandemic has had on the trial, to date, is the pause in recruitment which occurred March 2020 to July 2020, however, the trial is currently back recruiting in all sites. Some of the psychosocial intervention was delivered remotely (by telephone and video call) and some data collection was collected remotely during this time. The paper will include a summary of milestone dates such as the date COVID-19 was declared a pandemic by the World Health Organisation, date the Government imposed lockdown and dates the trial paused and restarted recruitment.

In addition, during the pandemic, changes to the distribution of medication for those in the oral arms of the study occurred. National clinical guidance was issued on 22 May 2020

indicating that rather than daily medication collection participants were to collect weekly and not be observed whilst taking them. This may have had an impact on some participants as they had access to more medication and more freedom with these (i.e. there was choice as to whether to take medication as directed). This could result in participants in these groups being more likely to disengage from treatment and relapse. However, subsequent guidance has recommended that supervision and dispensing interval should return to be determined on a case-by-case basis and informed by risk assessment [8]. This advice may change again in the event of a substantial increase in Covid-19 infection incidence.

Although these changes may have had an impact, investigators have no reason to believe that this will affect any signal (or no signal) detected.

However, baseline characteristics will be summarised by enrolment period (pre Covid-19, during Covid-19, post Covid-19) to assess if there are any relevant differences in the recruited population relative to the pandemic periods [9]. If deemed necessary sensitivity analysis adding 'pandemic enrolment period' into the model will be run and if found to be significant subgroup analysis may be conducted.

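### The COVID-19 check gates on the enrolment-period term, which cannot tell a shift common to both arms from a change in the treatment effect

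*SAP*

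**What the plan says.** The COVID-19 part of SAP 6.9 reports that "changes to the distribution of medication for those in the oral arms of the study occurred". Under guidance dated 22 May 2020, "rather than daily medication collection participants were to collect weekly and not be observed whilst taking them". The SAP then names a consequence: "This could result in participants in these groups being more likely to disengage from treatment and relapse". It adds that later guidance returned supervision and dispensing interval to individual decisions, and concludes that "investigators have no reason to believe that this will affect any signal (or no signal) detected".

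The planned check has three steps:

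1. Baseline characteristics are summarised by enrolment period, with three levels (before, during and after Covid-19) and no calendar dates.
2. If it is thought necessary, "sensitivity analysis adding 'pandemic enrolment period' into the model will be run and if found to be significant subgroup analysis may be conducted".
3. Missing data are also examined by enrolment period.

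The primary model in SAP 6.6 contains treatment and the stratification factors: "The randomisation stratification variables (centre and current injecting status) will be included in the model as covariates". The subgroup list in SAP 6.8, introduced by "Subgroup analyses will be conducted for the primary objective/outcome on the following", covers cocaine use, length of time in treatment, benzodiazepine use and CGI-S. Enrolment period is not on it. Protocol 12.2 mentions interaction tests for medication preference. Neither document mentions one for enrolment period.

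**The concern.** The SAP describes a mechanism that acts on the comparator. If weekly, unobserved collection makes oral-arm participants do worse, the difference between BUP-XR and oral treatment is larger while that practice lasts. That is a question about treatment by period.

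The term added to the model answers another question: whether abstinent days, averaged over the two arms, differ between enrolment periods. Allocation in phase 1 is 1:1 within site, so period should be nearly independent of arm. Adjusting for it should then hardly move the estimated treatment effect, even if that effect differs between periods. The significance of the period term nevertheless decides whether anyone looks at the effect by period, and even then the look is optional.

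At stake is how the main result is read. If part of the BUP-XR advantage reflected temporary comparator care, a reader would want to see that. If it did not, a reader would want the evidence, and a period covariate does not supply it.

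**Working it through.** The SAP gives no figure for this check. The only plan figure used is the sample size, which is reproduced first.

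**Sample size (SAP 4.1).** Inputs: rate 0.6, rate ratio 1.23, two-sided 5%, 90% power, 15% attrition. Exposure is read as 161/28 = 5.75 months; the 28-day month is inferred from the reference-trial example.

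- n per arm = (1.960 + 1.282)² × (1/0.6 + 1/0.738) / (5.75 × (ln 1.23)²) = 128.85, so 129.
- Total 258; 258/0.85 = 303.5, so 304. This matches.

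**What each term estimates.** Let abstinent days in the middle period fall by a in the oral arm and by b in the BUP-XR arm, with equal arms.

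- Period main effect: (a + b)/2.
- Change in treatment difference (interaction): a − b.
- Common shift (a = b): the main effect is a and the interaction is 0.
- Oral arm only (b = 0): the main effect is a/2 and the interaction is a.
- Opposite shifts (b = −a): the main effect is 0 and the interaction is 2a.

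The interaction contrast has twice the standard error of the main-effect contrast. For an oral-only change, effect and standard error therefore both double and the test statistic is the same. A two-period illustration with 258 participants and SD 55 shows this. The main-effect SE is 55 × √(2/129) = 6.85 days and the interaction SE is 13.7 days. A 20-day oral-only fall gives 10/6.85 = 20/13.7 = 1.46, which is 31% power for both tests.

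**Three periods, as in the SAP.** Assumptions that are not in the documents: equal thirds per period, SD 40 to 55 days, normal errors, 304 participants. The control mean is 0.6 × 161 = 96.6 days and the treated mean is 1.23 × 96.6 = 118.8, a difference of 22.2. Each scenario was simulated 2,000 times, with an F test for period and one for period by arm.

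| Change in the middle period | Treatment difference (days) | Period term significant, SD 40 / 55 | Interaction significant, SD 40 / 55 |
|---|---|---|---|
| None | 22.2 throughout | 5% / 5% | 4% / 4% |
| Both arms fall 20 | 22.2 throughout | 97% / 75% | 5% / 5% |
| Oral arm alone falls 20 | 22.2 to 42.2 | 43% / 24% | 44% / 25% |
| Oral falls 15, BUP-XR rises 15 | 22.2 to 52.2 | 5% / 4% | 80% / 50% |

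**Closed-form check.** With n = 304/3 per period, the noncentrality is n × (2/3) × ((a + b)/2)² / SD² for period and n × (2/3) × ((a − b)/2)² / SD² for the interaction. At SD 40:

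- A common 20-day fall gives 16.9 for period (96% power).
- A 20-day oral-only fall gives 4.2 for both terms (43% each).
- Opposite 15-day shifts give 0 for period and 9.5 for the interaction (79%).

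These agree with the simulation.

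**Scale.** These figures are in days, whereas SAP 6.6 uses a log link. A common 20-day fall leaves the difference at 22.2 days but moves the rate ratio from 1.23 to (118.8 − 20)/(96.6 − 20) = 1.29. The same ambiguity arises if both arms fall by an equal percentage, because the ratio then stays fixed. The fix should therefore state the scale.

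**Who was exposed.** The SAP puts the recruitment pause at March to July 2020, and the guidance of 22 May 2020 falls inside it. Counting back 168 days gives 6 December 2019. Anyone randomised from about then until the pause had some of days 8-168 on or after 22 May, yet may be labelled as enrolled before Covid-19.

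**The case against.** Four replies deserve weight.

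*The gate is not blind to the change the SAP describes.* This stands. A reader might infer from the halved coefficient that an oral-arm-only change would usually slip past the period term while an interaction test would catch it. The standard error is halved too, so the tests have about equal power (24-43% against 25-44%). What the period term lacks is the ability to say which kind of shift it has seen.

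*The plan has a second step.* This also stands. A reader might infer that the plan cannot show a changed treatment effect at all. That holds for the gating term only. A subgroup analysis by period, if done, could show differing effects, and a gate opened by a common shift would lead to much the same output as the fix. The step remains discretionary, however, and no between-period contrast is specified for it.

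*The covariate serves another purpose.* Its sentence follows a check for differences in the recruited population, and adjustment is a coherent response to changing case mix. That justifies keeping the covariate model. It does not make the period term a check on the dispensing mechanism.

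*The SAP expects no effect on the signal, and the change was not absolute.* The text is tentative: it speaks of a possible effect on some participants, and take-home doses were already allowed according to clinical response (SAP 4.4). It does not say in terms that the oral arms alone were affected, although it reports no dispensing change for BUP-XR. This limits how large an effect one should expect. The expectation itself is stated without supporting analysis, straight after a mechanism by which it could fail.

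**Conclusion.** The point holds in a limited form. The mechanism in SAP 6.9 is a treatment-by-period question, and the planned gate is a period main effect. It can open with no change in the treatment difference (75-97% of runs for a common 20-day fall) and stay shut under a large change (4-5% for opposite 15-day shifts). For an oral-only fall it does as well as an interaction test, so the defect is lack of specificity.

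The direction of the algebra needs only roughly equal arms within each period. The percentages rest on assumed equal thirds, SDs of 40 to 55 days, the shifts chosen, no attrition and normal errors in days. None of these comes from the documents, and the actual split across periods is unknown.

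Severity is minor. A reader might infer that the main result or its power is compromised. The documents do not support that: this is a conditional sensitivity analysis, and the primary intention-to-treat comparison, its 5% level and the target of 304 do not depend on it.

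**What to change.** In SAP 6.9, replace the significance gate with a pre-specified model:

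- Add enrolment period and treatment-by-period to the primary model, using the SAP's three periods with their calendar cut dates stated.
- Report the treatment effect in each period and the interaction estimate, each with a 95% confidence interval, whatever the period term shows. Give them as rate ratios to match the primary model, with differences in days alongside if wanted.
- Use neither the main effect nor the interaction test as a gate.
- Label the analysis exploratory, because 304 was not sized for it.

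Optionally, add a version that classifies participants by the overlap of days 8-168 with the changed guidance, from 22 May 2020 to an end date that the sponsor must state, since the SAP gives none. This would capture people enrolled before the pandemic who were exposed during follow-up. Calendar overlap still does not identify whose dispensing actually changed.

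The cost is one model and a short table. The estimates will be imprecise. With about 304/6 = 51 participants per arm per period, the half-width of a period-specific interval is 1.96 × SD × √(2/50.7), or about 16 days at SD 40 and 21 days at SD 55. Wide intervals that include no change should not be read as evidence that the effect was stable.

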6.10 EXPLORATORY ANALYSES

As indicated in section 5.2, further analysis is to be conducted at a later date but will not form the results of the current analysis. A separate statistical plan detailing all other analysis will be written and published in addition to this SAP.

7. SOFTWARE

All quantitative analysis will be completed using STATA version 15 or later.

APPENDIX 1 – POISSON REGRESSION ANALYSIS DECISION TREE

APPENDIX 2 – OBJECTIVES AND ASSOCIATED OUTCOME MEASURES AND CHARACTERISTICS

APPENDIX 3 - OUTCOME MEASURES SUMMARY AND SCORING TABLE

APPENDIX 4 – ASSUMPTIONS OF MODELS

APPENDIX 1 – POISSON REGRESSION ANALYSIS DECISION TREE

[figure not shown]

Figure obtained from;

<https://pdfs.semanticscholar.org/8ab1/829f559b869eeb48e38f15c5d94dc957a0f5.pdf>

APPENDIX 2 – OBJECTIVES AND ASSOCIATED OUTCOME MEASURES AND CHARACTERISTICS

Objective	Outcome Measure	Time Period	End point	Variable Type	Analysis Model	Scoring
One - effectiveness of BUP-XR and MET/BUP-SL	Primary outcome					
	Number of days abstinent from heroin	Days 8 – 168	24 weeks	Count	Poisson Regression	Count of days abstinent
	Secondary outcomes					
	Number of days abstinent from cocaine	Days 8 – 168	24 weeks	Count	Poisson Regression	Count of days abstinent
	Number of days abstinent from Benzodiazepines	Days 8 – 168	24 weeks	Count	Poisson Regression	Count of days abstinent
	Longest time in days continuously abstinent from heroin	Days 8 – 168	24 weeks	Count	Poisson Regression	Max Count of days consecutively abstinent
	Longest time in days continuously abstinent from cocaine	Days 8 – 168	24 weeks	Count	Poisson Regression	Max Count of days consecutively abstinent
	Longest time in days continuously abstinent from Benzodiazepines	Days 8 – 168	24 weeks	Count	Poisson Regression	Max Count of days consecutively abstinent
Two – Safety profile	Number of safety events	Study enrolment to 24 weeks	24 weeks	Count	Descriptive	n/a
Three – Treatment retention	Total retention time	Days 8 – 168	24 weeks	Count	Poisson Regression	Count of Days enrolled in maintenance medication for OUD
	Survival time to study withdrawal	Randomisation date to first discontinuation	24 weeks	Time to event	Cox regression	Time to first discontinuation
Four – OUD and CUD remission status	SCID-RV interview	Baseline to week 24	12 weeks & 24 weeks	binary	(Binary) logistic regression	Remission status (Yes/No) indicated by SCID-RV (see appendix 3 for SCID scoring)

Objective	Outcome Measure	Time Period	End point	Variable Type	Analysis Model	Scoring
Five – Clinician rated impression of patient response to treatment	Clinical Global Impression scale (severity and improvement - CQI-S/CGI-I)	Baseline to week 24	24 weeks	Ordinal	Ordinal logistic Regression	See Appendix 3
	Addiction Dimensions for Assessment and Personalised Treatment (ADAPT)	Baseline to week 24	24 weeks	Continuous	GLM	See Appendix 3
Six – Patient reported recovery outcomes	Craving response using Craving experience questionnaire (CEQ-F)	Baseline to week 24	24 weeks	Continuous	GLM	See Appendix 3
	Visual analogue craving rating (Need) (VAS-N)	Baseline to week 24	24 weeks	Continuous	GLM	See Appendix 3
	Visual analogue craving rating (Want) (VAS-W)	Baseline to week 24	24 weeks	Continuous	GLM	See Appendix 3
	Social functioning using Work and Social Adjustment Scale (WASAS)	Baseline to week 24	24 weeks	Continuous	GLM	See Appendix 3
	Depression using Quick inventory of Depressive Symptomatology (QIDS-SR)	Baseline to week 24	24 weeks	Continuous	GLM	See Appendix 3
	Improvement and Recovery using Substance Use Recovery Elevator (SURE)	Week 4 to week 24	24 weeks	Continuous	GLM	See Appendix 3
	Patient Reported Outcome Status (severity and improvement - PRO-S/PRO-I)	Baseline to week 24	24 weeks	Ordinal	Ordinal logistic Regression	See Appendix 3
	Emotion regulation using the Difficulties in Emotion Regulation Scale- short form (DERS-SF)	Baseline to week 24	24 weeks	Continuous	GLM	See Appendix 3
	Alcohol quantity, maximum consumption (ALC-QF (TOP))	Baseline to week 24	24 weeks	Continuous	GLM	See Appendix 3

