8.1 Inclusion criteria

Inclusion criteria

1. Aged \geq 18 years (no upper age limit);
2. Current diagnosis of DSM-5 OUD via SCID-5-RV (moderate-severe at baseline for current episode);
3. Currently enrolled on Met (30mg/day or less) or sublingual Bup or Bup-NX (24mg/day or less) or Esp (18mg/day or less) and in the view of the clinician would be able to convert to XR-Bup within 7 days post randomisation;
4. Voluntarily seeking treatment and able to attend the clinic as required in the protocol;
5. Able to communicate in English to level required to accept standard care and psychosocial intervention;
6. Possession of a contactable personal mobile phone or landline telephone number and ability to nominate at least one locator individual with a verifiable address and a telephone number to assist with the arrangement of follow-up appointments;
7. Living circumstances judged to be of sufficient stability to be able to engage/adhere to the study protocol;
8. Is not pregnant (confirmed) or breast feeding and, if currently or intending to have potentially procreative intercourse, agrees to use a birth control method (either oral hormonal contraceptives, barrier [condom or diaphragm], or Nexplanon implant) for the duration of the study.

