6.7 ANALYSIS OF SECONDARY OUTCOMES

All secondary outcomes are to be analysed as the primary outcome including the randomisation stratification variables (centre and current injecting status) in the models. The model used will be based on the outcome measure (dependent variable) format and the distribution of the data.

- Count variables will be analysed using a Poisson regression model. As with the primary outcome measure the exact model to be used will be based on the distribution of the data following the decision tree in appendix 1, figure 1.
- Continuous measures will be analysed with a GLM to assess the differences between the means of the treatment groups. In addition to the randomisation stratification factors, the baseline measure scores of the associated outcome will be included in the models as covariates to account for the baseline scores.
- Binary variables will be analysed using a (binary) logistic regression model
- Ordinal variables will be analysed using an ordinal logistic regression model

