6.9 SENSITIVITY ANALYSES OR MODEL TESTING

Sensitivity analysis will be conducted on the primary analysis model including the variables that were identified as predictors of missingness as covariates in the model.

Additionally, sensitivity analysis may be required around any assumptions made for the primary analysis (e.g. outliers, data distributions) but will only be conducted if necessary. This will include a best-case worst-case analysis on the self-report missing data on the primary outcome. Best case would assume that patients did not use during any missing time periods and worst case would assume that they did use substances to evaluate any impact the imputed data may have had on the results.

Furthermore, the confidence of the reliability of the self-report will be checked by conducting a best-case worst-case sensitivity analysis on the UDS missing data for the TLFB outcomes.

For those who have a missing UDS, we will assume all missing as negative for one dataset and then for another dataset assume all missing as positive. Utilising this best –worst case scenario will provide a range of values between which the real outcome is likely to lie. The width of this range is likely to be influenced by many factors (including the COVID pandemic and not being able to collect the UDS).

Primary and secondary analysis will be conducted on an ITT basis (including all those randomised to be analysed. Sensitivity analysis may be conducted, if necessary, on protocol deviations or eligibility violations by removing them from the analysis set. This includes protocol deviations (but is not limited to) such as;

- Patients not receiving randomized allocation (per protocol analysis)
- Patients not receiving treatment within 7 days (per protocol analysis)
- Ineligible patients being randomised (mITT analysis)

Sensitivity analysis will be conducted on the patient's months in treatment (for current episode) at baseline by running the model including the variable as a factor.

Additionally, sensitivity analysis of the patient's preference of BUP-SL or MET will be conducted again by running the model including that variable as a factor. This will be conducted given that there is an adequate sample of data per group at each level of the variable (BUP-SL or MET) a sample of 50% – 60% in the MET group will indicate that we will run this sensitivity analysis.

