APPENDIX 3 - OUTCOME MEASURES SUMMARY AND SCORING TABLE

Definition	Scoring	Item coding	Subscales	Direction	Missing value rules	Thresholds
Standard Clinical Interview for Dependence – Research version SCID-RV						
No reference available; below scoring derived from MACRRO database						
Structured Clinical Interview for DSM-5 (SCID-5) is a semi structured interview guide for making the major diagnoses.	Two single item scales (one for opioid and one for cocaine). Remission status is to be calculated from the SCID. Remission is satisfied (i.e. 'yes') if no symptoms are present that is a score of 1 or lower is obtained. If a score of 2 or more is given then remission status is 'no'.	Items are coded on a 5 point scale based on number of symptoms present; no symptoms, 1 symptom, Mild (2 – 3), Moderate (4-5) and Severe (6 or more)	None found	Lower better	None found	None found
Clinical Global Impression scale (severity and improvement - CGI-S/CGI-I)						
Busner, J. and Targum, S.D., The Clinical Global Impressions Scale: Applying a Research Tool in Clinical Practice (2007). Psychiatry.						
Brief stand-alone assessment of the clinician's view of the patient's global functioning. The scale comprises two companion one-item measures evaluating the severity of psychopathology and change from the initiation of treatment.	Two single item scales (CGI-S and CGI-I). Both items individually scored on a 1 to 7 point scale. Total score is not to be calculated from the two scales. However, the two scale scores will range from 1 to 7.	The CGI severity ranges from 1 'extremely mild' to 7 'extremely severe'	1. Severity item)	(1 Lower better	None found	1 – Extremely mild 2 – Very mild 3 – Mild 4 – Moderately severe 5 – Severe 6 – Very severe 7 – Extremely severe
Addiction Dimensions for Assessment and Personalised Treatment (ADAPT)						
Marsden, J., et al., Development of the Addiction Dimensions for Assessment and Personalised Treatment (ADAPT). Drug Alcohol Depend. (2014), http://dx.doi.org/10.1016/j.drugalcdep.2014.03.018						

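### Cocaine use disorder (CUD) remission is scored in all randomised participants, so people without CUD at baseline count as remitted and the reported rate is not a remission rate

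*SAP*

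**What the plan says.** - **Entry.** Protocol 8.1 requires "Current diagnosis of DSM-5 OUD via SCID-5-RV (moderate-severe at baseline for current episode"). Neither 8.1 nor 8.2 requires or excludes CUD.
- **Outcome.** SAP 5.2 (Objective 4) and Appendix 2 make OUD and CUD remission a binary outcome at weeks 12 and 24, given as "Remission status (Yes/No) indicated by SCID-RV (see appendix 3 for SCID scoring").
- **Scoring.** SAP Appendix 3 describes "Two single item scales (one for opioid and one for cocaine"). The rule for both is "Remission is satisfied (i.e. 'yes') if no symptoms are present that is a score of 1 or lower is obtained", and "If a score of 2 or more is given then remission status is 'no". It does not ask whether the disorder was present at baseline.
- **Analysis set.** SAP 6.9: "Primary and secondary analysis will be conducted on an ITT basis (including all those randomised to be analysed").
- **Model.** SAP 6.7: "Binary variables will be analysed using a (binary) logistic regression model", with centre and current injecting status as covariates. The sentence that adds baseline scores, "the baseline measure scores of the associated outcome will be included in the models as covariates to account for the baseline scores", stands under continuous measures only.
- **Protocol model.** Protocol 12.2 lists the baseline score on the outcome among the primary-model covariates. It carries the same covariates into the secondary models, including logistic models for binary outcomes.
- **Status.** SAP 4.3 treats all secondary outcomes as exploratory.

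**The concern.** Remission presupposes the disorder. The rule works for OUD because everyone enters with it. For cocaine, someone with no cocaine symptoms at baseline and none at week 24 is recorded as a CUD remission. The published percentage in each arm would then depend partly on how many people entered without CUD, and a reader could not separate the two.

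There may also be a loss of sensitivity. People who can hardly fail to score 'yes' add similar numbers to both arms and bring the arms closer together. Nothing else in the SAP repairs this: the cocaine-use subgroup in 6.8 covers the primary outcome only.

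**Working it through.** The documents give no rate, effect size or power for CUD remission, so there is no plan figure to reproduce. The check has two parts.

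**1. The rate.** Take a participant with no cocaine symptoms at baseline and none at follow-up. Protocol 8.1 admits them if they have OUD, Appendix 3 scores them 'yes', and SAP 6.9 keeps them in the denominator. They count as a remission. This follows from the text alone.

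**2. The comparison under the SAP's model.**

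Inputs:
- q, the share with CUD at baseline: assumed, 0.3 to 0.9. Protocol section 7 says only that cocaine use and dependence is common.
- Remission among those with CUD: assumed p0 = 30% (oral) and p1 = 45% (depot).
- r, the share scoring 'yes' among those without baseline CUD: assumed 95% in both arms, so treatment does not act on this group.
- Evaluable per arm: 152 × 0.85 = 129, from the Phase 1 target and the 15% attrition allowance (Protocol synopsis and 12.1, SAP 4.1).
- Two-sided 5% test (SAP 4.3).

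Formulas:
- Arm rate in all participants = q·p + (1 − q)·r.
- Risk difference = [q·p1 + (1 − q)·r] − [q·p0 + (1 − q)·r] = q·(p1 − p0), so it shrinks by exactly the factor q.
- Power: normal approximation for two proportions, with n = 129 per arm for all participants and 129·q for those with baseline CUD. The stratification covariates are left out.

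At q = 0.5:
- Oral: 0.5 × 0.30 + 0.5 × 0.95 = 62.5%. Depot: 0.5 × 0.45 + 0.5 × 0.95 = 70.0%.
- OR, all participants: (0.70/0.30) / (0.625/0.375) = 1.40.
- OR, baseline CUD only: (0.45/0.55) / (0.30/0.70) = 1.91.

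| q | All participants | Risk difference (points) | OR, all | OR, CUD only | Power, all | Power, CUD only |
|---|---|---|---|---|---|---|
| 0.3 | 75.5% v 80.0% | 4.5 | 1.30 | 1.91 | 14% | 27% |
| 0.5 | 62.5% v 70.0% | 7.5 | 1.40 | 1.91 | 25% | 42% |
| 0.9 | 36.5% v 50.0% | 13.5 | 1.74 | 1.91 | 59% | 66% |

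If everyone without baseline CUD scores 'yes' (r = 100%), q = 0.5 gives 65.0% v 72.5%, OR 1.42 and power 25%.

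**Under the protocol's model.** Adding baseline CUD status to the logistic model at q = 0.5 and r = 95% gives an OR of 1.71 and power of about 36%. At r = 100% it gives 1.91 and 42%, the same as the restricted analysis. The oral-arm percentage in the table of results would still read 62.5% (or 65.0%), although remission among those with the disorder is 30%.

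**If treatment also acts on those without baseline CUD** (q = 0.5):
- 90% v 95% in that group: all-participant power is 39%, against 42% restricted.
- 85% v 95%: all participants 57.5% v 70.0%, OR 1.72, power 55%, against 42% restricted.

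**The case against.** The strongest case on the other side has four parts.

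- **Baseline adjustment may already be intended.** Protocol 12.2 puts the baseline score in the secondary logistic models, which would remove much or all of the illustrated loss. This stands as a limit on the dilution argument. It does not settle the matter, because SAP 6.7 gives baseline scores to continuous measures only, and it leaves the reported rate uncorrected.
- **Dilution and power loss are conditional.** A reader might infer that the all-participant analysis must have less power. It need not: in the 85% v 95% case above it has more. The inference requires no treatment effect in people without baseline CUD.
- **The all-participant comparison is valid in itself.** The proportion without current CUD among everyone randomised is a sound intention-to-treat contrast. That is right, but the quantity is not remission and should not carry that name.
- **The consequence is small.** The outcome is exploratory, and on these assumptions even the restricted analysis has only 42% power at q = 0.5. This stands, and it limits the importance of the point.

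A reader might also infer that people who never had CUD are being counted. The documents do not support that. The rule concerns symptoms at follow-up, and the people affected are those without CUD at baseline, who may include some already in remission at entry.

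Restriction might be said to break intention-to-treat. It does not, because baseline CUD is fixed before randomisation and all randomised participants who have it stay in their allocated arm.

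**Conclusion.** Wrong as written. Followed exactly, the SAP counts participants without CUD at baseline as CUD remissions, and no other text in either document prevents it. The error in the reported rate needs no assumption beyond some participants entering without CUD.

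The effect on the treatment comparison is conditional. It holds under the SAP's model (centre and injecting status only) and if treatment leaves the cocaine item unchanged in people without baseline CUD. The risk difference then shrinks by the factor q, and in the illustration the OR falls from 1.91 to between 1.30 (q = 0.3) and 1.74 (q = 0.9). Every rate in that illustration is assumed. Without a baseline CUD prevalence the true size is unknown, and it is small if nearly all participants have CUD. Under Protocol 12.2 much or all of the loss is recovered.

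OUD remission and the primary conclusion are unaffected.

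**What to change.** In SAP Appendices 2 and 3, and in 6.7:

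1. Restrict the CUD remission analysis at weeks 12 and 24 to all randomised participants with two or more cocaine symptoms on the baseline SCID-5-RV, and report that denominator by arm.
2. Describe CUD at follow-up among the other participants separately.
3. If an all-participant comparison is kept, label it 'no current CUD' and adjust it for baseline CUD status.
4. Reconcile SAP 6.7 with Protocol 12.2 on baseline adjustment for binary outcomes.

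The cost is SAP wording, agreed before unblinded analysis. No new data are needed, because the SCID-5-RV is already scheduled at baseline and weeks 12 and 24 (SAP 5.1, Table 1). The price is a smaller analysis set, and any effect on new CUD is described but not tested in this comparison.
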